9.2.4 Multiple visits

The procedure described above is carried out over 2 days. We know from practice that patients are usually treated by a physiotherapist 1-2 times a week. Thus, the subjects are measured 2x within the same week in order to be able to make a practical statement about possible lasting and/or cumulative effects.

At the end of both measurement days, he/she will receive the amount due to him/her according to the advertisement.

The lump sum is CHF 50.

SUPSI

9.3 Drug study

-

9.3.1 Definition and assessment of (serious) adverse events and other safety related events

-

9.3.2 Reporting of serious adverse events (SAE) and other safety related events

-

9.3.3 Follow up of (Serious) Adverse Events

-

9.4 Medical Device Category C studies

The Patello device is an innovative product that does not yet have CE certification. All individual components of the device are CE certified.

In this experimental study for the effectiveness study, 30 test subjects are to be tested. The study focuses on basic findings. It serves as proof of effectiveness. The monitoring for quality assurance is carried out by [name]. [name].

9.4.1 Definition and Assessment of (Serious) Adverse Events and other safety related events

An adverse event (ADVERSE EVENT) AE) is any unfortunate medical occurrence in a study subject who is exposed to the intervention (as listed in Chapter 8.1.1) that is not necessarily causally related to the study process. An AE can therefore be any adverse and unintended sign, symptom, or temporal illness with the use of an intervention product (according to Chapter 8.1.1), either or in relation to the medical intervention product (according to Chapter 8.1.1).

According to swissethics.ch, a serious adverse event (SAE) is classified as any unfortunate medical occurrence that results in death, is life-threatening, requires or prolongs hospitalization of the subject, results in a persistent or significant disability/inability, or is a congenital anomaly/birth defect. In our study, an SAE is not to be expected.

If the intervention leads to a side effect, this is classified as a safety-relevant event by the study leader. For the affected study participant, the study is completed at this time, and the data already collected will be processed as described in chapters 7.4 and 9.1.6.

On the last page of the subject-specific demographic data collection sheet, the following are recorded:

- Date and time of the incident
- Course of the incident
- Persons involved & witnesses
- Study ID (specified by the CEC)
- Personal data of the person concerned (if not previously recorded)

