8.5 Follow-up treatment of eliminated participants

Data already collected from eliminated participants will be evaluated as far as possible and will be included in the data analysis of the study.

There is no disadvantage for the participants if they discontinue their participation in the study and no further interventions are necessary for follow-up treatment.

If study participation was discontinued due to an excessive reaction/injury occurring during study participation, this will be recorded and reported to the sponsor investigator (head of the research laboratory), who is also the study leader, and the supervisor of the study. If medical care is necessary, the report is forwarded to the business liability insurance of Thim van der Laan AG (Basler Versicherung) in order to ensure the appropriate follow-up treatment.

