9.1.6 Collection of data in case of early termination of studies

For the participants, there is no disadvantage in the event of an (arbitrary) discontinuation of study participation and no further interventions are necessary for follow-up treatment. The data collected to date will be evaluated as far as possible and included in the data analysis (in accordance with Art. 9 ClinO).

If study participation was discontinued due to an excessive reaction/injury occurring during study participation, this will be recorded and reported to the sponsor investigator (head of the research laboratory), who is also the study leader, and the supervisor of the study. In the event of necessary medical treatment, the report is sent to the business liability insurance of Thim van der Laan AG (Basler Versicherung).

The following are recorded:

- Date and time of the incident
- Course of the incident
- Persons involved & witnesses
- Study ID (specified by the CEC)
- Personal data of the person concerned (if not previously recorded)

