9.4.2 Reporting of (Serious) Adverse Events and other safety related events

In accordance with Art. 37, Art. 42, Art. 43

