9.4.3 Follow up of (Serious) Adverse Events

A safety-related event is logged and immediately reported to the sponsor investigator (head of the research laboratory), who is also the study leader, and the supervisor of the study.

SUPSI

The CEC will be informed as soon as possible and appropriate changes will be made to the protocol of the study. Further explanations can be found in chapter 2.10. Safety and protective measures must be reported to the responsible CEC within two days.

The report continues to the business liability insurance (Basler Versicherung) of Thim van der Laan AG in Landquart.

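### Adverse events are defined regardless of cause, but the protocol's text records only attributed side effects and reactions or injuries that ended participation

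*Combined protocol and SAP*

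**What the plan says.** The definition in section 9.4.1 covers any untoward medical occurrence in an exposed subject, including one "that is not necessarily causally related to the study process".

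The rules that lead to a record are these:

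- Section 9.4.1: "If the intervention leads to a side effect, this is classified as a safety-relevant event by the study leader". The next sentence adds "For the affected study participant, the study is completed at this time". A new paragraph then begins "On the last page of the subject-specific demographic data collection sheet, the following are recorded" and lists the particulars of an incident, a term the protocol does not define.
- Section 9.4.3: "A safety-related event is logged and immediately reported to the sponsor investigator", who is also the study leader, and to the study supervisor.
- Section 9.1.6: "If study participation was discontinued due to an excessive reaction/injury occurring during study participation, this will be recorded and reported". Section 8.5 carries the same condition.
- Section 9.4.2, on reporting, reads only "In accordance with Art. 37, Art. 42, Art. 43".

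Nothing elsewhere collects events routinely. Section 9.1.5 limits safety data to the health questionnaire, 9.1.5.1 (unfavourable events) holds a dash, 5.2 says nothing further is recorded for safety, and 10.3.5 plans no safety analysis.

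**The concern.** The definition and the recording triggers do not match. The definition applies before anyone judges cause. The 9.4.1 trigger applies only after that judgement, and the 8.5 and 9.1.6 trigger applies only once participation has stopped.

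The mismatch matters more here than in many studies. There is no control group (8.1.2, 8.2.2) against which to check an attribution, and 6.1.2 says examiners cannot be blinded to the intervention. The person who classifies the event is the study leader, who is also the sponsor-investigator. Under 9.4.1, classifying an event as a side effect also ends that participant's study, and 10.4 allows no replacement, so each attribution costs data in a study of 30.

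Debatable mild events are plausible. Section 3.7 foresees skin irritation and paraesthesia, and 8.3 builds the pressure up to each subject's tolerance limit. Harm is a ground for stopping the study in 2.9, and evidence of harm depends on what was written down.

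**Working it through.** The documents give no event rate, event count or safety threshold, so there is no planned figure to reproduce. The check compares the passages and then gives an illustration under assumed values.

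**Step 1: the rules side by side.**

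| Section | What sets it off | Cause required? | End of participation required? |
|---|---|---|---|
| 9.4.1, definition | any untoward occurrence in an exposed subject | no | no |
| 9.4.1, classification | side effect of the intervention, judged by the study leader | yes | no, but it follows from the next sentence |
| 9.4.3, logging | a safety-related event; the only classification rule for this is the line above | yes, by that link | no |
| 8.5 and 9.1.6 | excessive reaction or injury during participation that led to discontinuation | not for an injury | yes |
| 9.1.5, 9.1.5.1 | nothing beyond the health questionnaire; blank | – | – |

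**Step 2: follow an event through the rules.** An event attributed to the device is classified under 9.4.1 and logged under 9.4.3. A reaction or injury that ends participation is recorded under 8.5 and 9.1.6, whatever caused an injury. Take instead an ache that arises between the two measurement days, is put down to sport, and does not stop the subject from returning. It meets the definition and none of the triggers. The recorded set is therefore filtered by cause or by discontinuation.

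**Step 3: which events the incident list in 9.4.1 belongs to.** It follows directly after the side-effect sentences, and 9.1.6 has the same list for a discontinuation. Both facts tie it to an attributed or participation-ending event, although its own wording states no condition.

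**Step 4: illustration.** From the documents: n = 30 (section 10.1). Assumed: a share p of subjects has an event as defined, a share c of those events meets a trigger, and subjects are independent with at most one event counted each. Then

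- expected events as defined = 30p
- expected events recorded = 30pc
- P(none recorded) = (1 − pc)^30

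For p = 0.10, 30 × 0.10 = 3.0 events are expected. With c = 0.50, 30 × 0.05 = 1.5 are recorded and P(none) = 0.95^30 = 0.21. With full recording, P(none) = 0.90^30 = 0.04.

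P(none recorded) over a range:

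| p | c = 0.25 | c = 0.50 | c = 0.75 | c = 1 |
|---|---|---|---|---|
| 0.05 | 0.69 | 0.47 | 0.32 | 0.21 |
| 0.10 | 0.47 | 0.21 | 0.10 | 0.04 |
| 0.20 | 0.21 | 0.04 | 0.01 | 0.001 |

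Over p from 0.05 to 0.20 and c from 0.25 to 0.75, expected recorded events run from 0.4 to 4.5, against 1.5 to 6.0 as defined. Since c cannot exceed 1, recorded events never exceed defined ones.

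**The case against.** The strongest reply is that no event count is planned. Section 10.3.5 provides no safety analysis and 5.2 names no safety outcome, so there is no planned estimate to bias. The description of risk as small in 3.7 is a prior expectation, and 2.9 ties stopping to no count. This stands. It limits the point to the event record and to later uses of it.

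The incident list in 9.4.1 could also be read as covering every adverse event, because it is a separate paragraph under a heading that names adverse events generally. Likewise, the logging sentence in 9.4.3 does not itself mention cause. These readings are possible but less natural, and an ambiguous trigger would need rewording anyway.

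The articles cited in 9.4.2, and the standards to which 2.5 commits, may add documentation duties. Their text is not in the documents, so this can be neither confirmed nor ruled out.

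Discomfort is scored from 0 to 10 at all six measurements on each day without any attribution step, so an ache during a session may leave a trace. That is true, but the score is not an event record and cannot show what happened between the two days. Reports also go to the study supervisor, which gives a second reader, though only for events that have already met a trigger.

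**Conclusion.** The inconsistency is real and should be corrected. On the most natural reading, an event that meets the definition but is neither attributed to the device nor ends participation has no written route to the data sheet. The direction is certain on that reading: the record can only under-represent events as defined. The size is unknown. The 0.21 against 0.04 rests on an assumed 10% rate and an assumed 50% capture.

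The documents do not support three stronger readings that a reader might infer:

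- **That the study will report a biased event rate and make the device appear safer.** No rate is planned. This would happen only if the incident pages were later summarised as the safety result.
- **That all recorded events are selected by cause.** The rule in 8.5 and 9.1.6 selects an injury by discontinuation and timing.
- **That an empty record would wrongly exclude a high true rate.** For 0 of 30 the exact two-sided upper 95% limit is 1 − 0.025^(1/30) = 11.6%. That limit describes events meeting a trigger, so it does not contradict an all-cause rate of, say, 20%. It misleads only if one is presented as the other.

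**What to change.** Leave the side-effect sentence and the participation rule in 9.4.1 as they stand. Simply widening the side-effect condition to every adverse event would attach the next sentence, which ends the participant's study, to every such event.

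Add a separate recording sentence to 9.4.1, cross-referenced from 8.5, 9.1.5.1 and 9.1.6: every adverse event as defined in 9.4.1, on or between the two measurement days, is asked about at each visit and entered on the existing event page, whether or not it is attributed to the device and whether or not participation continues.

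Add relatedness to that page as its own field, judged after the entry is made. Amend 10.3.5 to a descriptive listing of all events and, separately, of related events.

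The cost is wording in five sections, one extra field and one short question per visit. The downside is a few trivial unrelated entries and a less favourable raw event list.

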3.7 Risk / Benefits

The possible occurrence of risks from the use of the Patello is to be assessed as small: short-term skin irritations and/or paraesthesia could occur.

The subjects do not benefit from participating in the study. The study serves to prove the effectiveness of the Patello device. If this is the case, the device can be used in the rehabilitation process of patients with the above-mentioned knee joint problems.

Justification of the choice of population

This series of studies will be conducted with healthy adults to assess the extent of the Quantify displacement of the kneecap by means of the patello.

Table 1: Overview of inclusion and exclusion criteria

Inclusion Criteria	Exclusion criteria

- Adults aged 18 to 30 Years- No surgical interventions and/or current complaints (pain at rest or during exertion) on the musculoskeletal apparatus in the area of the lower extremities- closed, intact skin conditions in the knee and thigh area- Don't be afraid of the intervention	
- Adolescents and adults over 30 years of age- Surgical interventions and/or current complaints (pain at rest or during exertion) on the musculoskeletal Apparatus in the area of the lower extremities- no closed, intact Skin conditions in the knee and thigh area- Fear of intervention

The test subjects are comprehensively informed about the course of the study and possible risks before they are accepted to participate in the study. You will also receive the information in written form and have the opportunity to ask questions if anything is unclear. The declaration of consent explains to them what their rights and obligations are when participating. In addition, they are informed that they may withdraw from participation at any time without giving reasons, without incurring any disadvantages as a result.

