5.2 Secondary outcomes

Subjective information on general well-being

The secondary outcome, the recording of the subjective well-being of the test person, is determined using a visual analogue scale (VAS scale 0 - 10) and reflected in the number of cm. The value "0" describes "maximum feeling of well-being", the value "10" a "maximum feeling of discomfort". The value is considered a subjective parameter.

Security considerations

SUPSI

No further results are recorded that would serve safety.

Discontinuation of the experiment is the responsibility of the examiner with regard to the subject's subjective feelings and expressions.

If a test subject does not feel comfortable during the intervention according to his or her subjective assessments, he or she can discontinue the experiment and withdraw participation in the study without any disadvantages.

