8.4 Adherence to the study intervention

The test subjects are not unnecessarily distracted by the examiners or the study director with conversations. Communication is kept to a minimum, only study-related discussions are held in order not to influence the results and to ensure homogeneity.

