8.6 Preventive measurements

The questionnaire determines the eligibility to participate in the study by recording the inclusion and exclusion criteria.

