8.7 Accompaniments

No further side effects are expected from study participation.

SUPSI

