9.1.4 Collection of further results

No further results will be collected.

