9.1.5 Collection of safety parameters

No safety parameters are collected except for the health questionnaire.

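### Section 9.4.1 stops a participant for any side effect of the device, but no scheduled step looks for the two effects foreseen in 3.7, and skin is not rechecked before day 2

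*Combined protocol and SAP*

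**What the plan says.** Section 9.4.1 has the study leader classify a side effect of the intervention as a safety-relevant event, without any severity threshold, and adds: "For the affected study participant, the study is completed at this time". Data already collected are kept under 7.4 and 9.1.6.

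On what to expect, section 3.7 says the risk "is to be assessed as small: short-term skin irritations and/or paraesthesia could occur", and section 8.7 adds: "No further side effects are expected from study participation".

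On what is recorded:
- Section 9.1.4: "No further results will be collected".
- Section 9.1.5: "No safety parameters are collected except for the health questionnaire". Section 9.1.5.1, on adverse events, contains only a dash.
- Section 5.2: "No further results are recorded that would serve safety".
- Section 10.3.5 plans no safety analysis.

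The questionnaire is a screening form. Section 8.6 says: "The questionnaire determines the eligibility to participate in the study by recording the inclusion and exclusion criteria". Closed, intact skin at the knee and thigh is an entry criterion (7.1), so it is settled once, at screening.

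Section 9.2.4 carries out the same procedure on both days, with a break of at least two days (9.2.1). Settings are redefined each day (3.6), and mobilisation pressure is built up to the subject's tolerance limit (9.2.3).

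**The concern.** Stopping at any side effect is a defensible rule for healthy volunteers who gain nothing from taking part. To work evenly, such a rule needs a way of finding the side effects, and the plan names two foreseeable ones without scheduling a look or a question for either.

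Three things are at stake. Two subjects with the same mild reaction may be treated differently because one reaction happened to be noticed. A subject with skin still irritated from day 1 could start day 2 without anyone being required to look at the knee. And for a device that is not CE certified as a whole, the trial could report only the events that came to attention, not how many of 30 subjects had each effect when asked and examined.

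**Working it through.** **Step 1: the schedule.** Tables 2, 4 and 5 (sections 6, 9.1 and 9.2.3) list information, consent, demographics, intervention, ultrasound image and well-being. With 6 measurements on 2 days, each subject has 6 × 2 = 12 measurement points. Scheduled skin or paraesthesia checks at these points: 0. Scheduled checks in the preparation in 9.2.2, which also serves day 2: 0.

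**Step 2: what the existing safeguards cover.**

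| Safeguard | Where | What it does | What it leaves open |
|---|---|---|---|
| Discomfort VAS, asked orally at each measurement | 9.1.3, 11.2.1, tables | Gives one overall score | Specific to neither effect; no stop threshold |
| Examiner's stopping duty; subject may stop | 5.2 | Acts on feelings and expressions | No prompt to look at skin or ask about tingling |
| Emergency stop on the hand control | 3.2, 8.1.1 | Releases the grippers | Records nothing |
| Incident page on the demographic sheet; immediate reporting | 9.4.1, 9.4.3 | Documents an event | Only one already noticed |
| Refitting of pressure on each day | 3.6, 9.2.2 | Adapts to well-being | Does not require skin to be inspected |

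Some events would be found by these routes. None is aimed at the two foreseen effects.

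**Step 3: how far zero recorded events would reassure (illustration).** The documents give neither a reaction rate nor the share of reactions that would be noticed. Let s be an assumed share noticed.

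- One-sided 95% upper limit for 0 of 30: 1 − 0.05^(1/30) = 0.0950. Divided by s, this is 9.5% (s = 1), 12.7% (0.75), 19.0% (0.5) or 38.0% (0.25).
- If 10% of subjects truly react (assumed), the chance of recording none is (1 − 0.1s)^30: 0.042, 0.096, 0.215 or 0.468 for the same values of s.

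These figures show the direction only. The conclusion rests on steps 1 and 2.

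**Step 4: cost to the primary analysis if checks lead to more stops.** The synopsis gives n = 30, effect size 0.68 and power 0.95. It does not name the test or its sidedness. A two-sided paired t-test at alpha 0.05 (noncentral t, n − 1 degrees of freedom, noncentrality 0.68 × √n) gives 0.949 at n = 30, which reproduces the stated figure; a one-sided test gives 0.977 and does not. With 3 subjects lost (10% of 30, assumed) n = 27 gives 0.925. With 6 lost (20%, assumed) n = 24 gives 0.891.

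These losses are pessimistic. A stop at the end of day 1 or before day 2 leaves all six day-1 measurements complete, and 10.2 and 10.4 keep complete interval data.

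**The case against.** The strongest reply is that sessions are supervised and the knee is in view. The subject wears shorts, an examiner images the patella at every measurement, and a discomfort score is asked 12 times. The examiner must act on how the subject feels, the subject can stop, and 9.4.1 provides an incident page. The foreseen effects are short-term and at least two days separate the sessions. A reaction noticed on day 1 has already ended participation. Estimating a reaction frequency is not an objective of the trial. All of this stands, and it makes the point minor. It does not supply a step that looks or asks for the two effects, and painless redness or mild tingling need not move a general discomfort score.

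A reader might draw stronger conclusions that the documents do not support:

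- **That there are two conflicting stop rules.** Sections 8.5 and 9.1.6 speak of discontinuation for an excessive reaction or an injury. They are conditional: they say what is recorded and reported after such a stop, not when to stop. Only 9.4.1 links a side effect to the end of participation.
- **That effects surface only by chance or unprompted.** The repeated VAS and the examiner's duty in 5.2 contradict this.
- **That subjects are discouraged from speaking.** Section 8.4 says "Communication is kept to a minimum, only study-related discussions are held in order not to influence the results". Mentioning tingling is study-related, so this is weak evidence of missed events.
- **That the forms certainly lack such an item.** The enclosed data forms (11.1.2) and the monitoring text were not available. The incident page shows that safety entries on forms are possible despite 9.1.5. Nothing in the available text points to a skin recheck.

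**Conclusion.** The point holds as a minor safety and conduct improvement. The plan stops participation for any side effect and foresees two. It schedules no specific check for either at 12 measurements per subject, and none before day 2. This follows from the text and needs no assumed rate.

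Its size in affected subjects cannot be estimated from the documents. The upper limits and probabilities shown depend on an assumed share noticed and, for the probabilities, an assumed 10% reaction rate. It would be wrong to infer that the primary result is biased or underpowered: even with 3 to 6 subjects lost entirely, power at the synopsis effect size would be 0.925 to 0.891, if the test is a two-sided paired t-test on complete subjects.

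**What to change.** 1. On each day, after measurement 6 and its VAS value have been recorded and the grippers released, inspect the contact skin and ask once about paraesthesia. Enter two yes/no items on the existing data sheet; a yes goes to the study leader for classification under 9.4.1.
2. Before day 2, repeat both items and confirm that the skin meets the 7.1 criterion. If it does not, do not start.
3. Report the number of subjects with each effect.

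Do not add questions between measurements. Prompts would accumulate with the number of mobilisations and could influence the later VAS values that 10.1 compares with the single-mobilisation value. The question at the end of day 1 and the one before day 2 precede all day-2 VAS values alike, so they do not track repetition within a day, though a comparison of VAS between days could be slightly affected.

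Cost, at an assumed half minute per check: 3 × 0.5 = 1.5 minutes per subject, and 30 × 1.5 / 60 = 0.75 staff hours. No extra subjects, staff or visits. The downside is that a few more subjects may be stopped under 9.4.1.

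Optionally, align the wording in 8.5 and 9.1.6 with 9.4.1. This is a tidy-up, not a correction of a contradiction.
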